4.3 Early Withdrawal of Subjects

4.3.1 When and How to Withdraw Subjects

Participants may be withdrawn from the study if they are disruptive during the group discussions or cannot be contacted by the study staff after initial contact.

5 Study Procedures

AIM 1a: Collect key qualitative data on determinants (facilitators and barriers) of success in maintaining the functional benefits of obesity treatment over time.

Interview Participants: The [name] Nutrition Lab at Duke University currently have two ongoing weight loss interventions in obese, older adults. We will contact our past participants, who previously agreed to be contacted for future research study, and successfully completed a lifestyle intervention (lost at least 3% body weight and increased short physical performance battery (SPPB) score by 1 point or 6-minute walk test (6MWT) by 50 meters) within the last 6 to 18 months. Participants who pass the telephone screen are willing to participate will be consented (Table 1), weighed, and complete the SPPB and 6MWT to determine their current functional status. Participants will then be separated into one of two groups, **Maintainers** or **Non-maintainers**, based on their current functional status (Table 2; n=12 to 15 per group or until thematic saturation is reached in each group). Next, semi-structured interviews will be conducted to identify personal beliefs, behaviors, and environmental factors that facilitated their success or treatment relapse.

Table 1. Inclusion/Exclusion Criteria Aim 1a

Inclusion Criteria	Exclusion Criteria

 Participated in a weight loss intervention in the last 6 to 18 months and lost \geq 3% body weight and improved SPPB score by \geq 1 point or 6MWT by \geq 50 meters (Perera et al. J Am Geriatr Soc. 2006;54(5):743-9) Age \geq 60 Able to speak and understand spoken and written English. 	
 Presence of unstable or symptomatic life-threatening illness Neurological conditions causing functional impairment, including Parkinson's disease, multiple sclerosis, and permanent disability due to stroke Inability to complete physical function assessment Unwilling to have their individual interview audio recorded History of cognitive impairment

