8. What were your expectations of losing weight?
 - a) What were you hoping to change, achieve?
 - b) Were those expectations met? Not met?
9. Has COVID-19 impacted your nutrition and/or physical activity? If so, how? If not, why?

Environment

1. How does your family/friends influence your eating/exercise habits?
2. What do you feel are your main barriers to healthy eating/exercise?
3. How does your culture/community affect your eating/exercise habits?
4. While you were participating in the _____ study, where did your support come from?
5. When you were in the study how did your social support network (friends, family, colleagues) react?

AIM 1b: Develop novel, customizable tele-programs of nutrition and exercise to maintain and extend legacy benefits of a recent obesity intervention: Creation of tele-intervention protocols for testing

The information gained from the individual interventions, combined with our expertise in nutrition and exercise interventions in obese, frail older adults and our established experts in tele-health and behavior science will inform the content of Tele-nutrition and Tele-exercise Legacy Intervention. Furthermore, protocol development for the Legacy Intervention will employ Social Cognitive Theory³ components that are key to maintaining behavior change. Expected Findings: we anticipate the “Legacy Intervention” will include cognitive behavioral strategies (e.g., goal setting, self-monitoring, and social support) and draw upon a toolbox of e-approaches, including daily and weekly text reminders, virtual exercise classes, virtual individual and group nutrition classes, and step tracking device.

AIM 2: Determine the feasibility, acceptability, and fidelity of a 3-month lifestyle enhancing tele-intervention: Pilot intervention trial

The 3-month tele-nutrition and tele-physical activity intervention developed in Aim 1b will be pilot-tested in older adults who, within the last 3 months, successfully completed a lifestyle intervention and meet the inclusion criteria in Table 3.

Successful completion of a lifestyle intervention: lost at least 3% body weight and increased SPPB score by 1 point or increased their 6MWT by 50 meters from their baseline.

We will enroll participants until we reach a total of 10 study completers. We anticipate enrolling approximately 15, allowing for a 30% dropout rate.

Table 3. Inclusion/Exclusion Criteria Aim 2

Inclusion Criteria	Exclusion Criteria

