
 Participated in a weight loss intervention in the last 3 months and lost $\geq 3\%$ body weight and improved SPPB score by ≥ 1 point or 6MWT by ≥ 50 metes (Perera et al. J Am Geriatr Soc. 2006;54(5):743-9) Age ≥ 60 Able to speak and understand spoken and written English. Able to record dietary intake and weight 	
 Presence of unstable or symptomatic life-threatening illness Neurological conditions causing functional impairment, including Parkinson’s disease, multiple sclerosis, and permanent disability due to stroke Inability to complete physical function assessment No access to internet connection to participate in the tele-intervention Unable or unwilling to use provided tablet to participant in tele-intervention History of cognitive impairment

Setting: Screening will be conducted by telephone. Consents will be sent electronically and a consent presentation will be conducted virtually using Duke Zoom. Consented participants will come to the Duke Center for Living Stedman Center to receive their tablet and Garmin watch and will be provided an overview of how to login to the tele-intervention. All additional interaction will occur virtually.

Measurements:

Baseline: Baseline outcomes will be assessed after participant picks up tablet and Garmin watch. Using Duke Zoom, participants will be guided through their functional assessment and will be asked to complete their questionnaires using a REDcap link that was sent to them. Midpoint (6 weeks) and Endpoint (12 weeks): outcomes will be collected virtually as they were at baseline

Outcome Measures

Table 4: Aim 2 Outcome Measures and Collection Points

Measurement/Procedure	Time Points	Method
Function and Activity		
SPPB	0, 6, 12 weeks	Balance (side-by-side, semi-tandem, tandem), gait speed (3-meter timed walk), strength (chair stands).
6-minute walk test (aerobic endurance)	0, 6, 12 weeks	Farthest distance walked as possible in 6 minutes (measured using Garmin watch)
Average Step Count	Weekly	Average weekly step count will be determined using Garmin VivoSmart3 watch
Body Weight and Diet		
Body weight	Weekly	Same scale, light clothing and no shoes, measured to nearest 0.1 kg
3-day diet record; Daily food journal (Adherence)	0, 6, 12 weeks	3-day diet record by multiple pass; analyzed Food Processor (Version 10.13, 2013; ESHA Research); Daily food journal assessed by registered dietitian
Function, body composition		

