Low-Intensity Chair Tele-Exercise: All physical activity and exercise involves some risk; however, the low-intensity chair exercises will be lead by trained certified group exercise instructors and carefully designed to ensure maximum safety. Participants will be instructed to only do the activities they feel comfortable doing and will be asked to provide their rate of perceived exertion multiple times throughout the exercise class to allow for close monitoring. Furthermore, the exercise prescription described in the present study approximate the standard physical activity recommendations for older adults. The most common adverse consequences associated with participation in physical activity are fatigue, muscle soreness.

Participants will be provided contact information for [name] and all study team members and encouraged to communicate with them about any concerns regarding any aspects of the study. All reported events will be recorded in the adverse event log (including the subject's name, date, and event description) and the PI and study team will be notified. All health occurrences will be recorded and regularly reviewed by the study staff and reported to the IRB according to IRB guidelines.

Psychological Risks

Semi-Structured Interviews: Participants may feel uncomfortable by questions asked during interview. We will inform all participants that they can refuse any of the questions at any time during the study and they will be allowed to take a break during the interview if needed.

Legal Risks

The present study poses no legal risks to participants.

Economic Risks

The present study poses no economic risks to participants.

Social Risks

Loss of confidentiality is always a potential risk and every effort will be made to keep participant information confidential. To reduce loss of confidentiality, participants will be instructed to not use the provided tablet for personal use. Furthermore, the tablet will be cleaned to remove any personal information.

Vulnerable Populations

Vulnerable populations will not be eligible for participation in this study.

Alternatives to Participation

The only alternative is non-participation. Participants may choose not to participate in the study, or, if they agree to participate in the study, they may withdraw from the study at any

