time. Their decision not to participate or to withdraw from the study will not involve any penalty or loss of benefits to which they are entitled, and will not affect their access to health care at Duke. If they withdraw from the study, no new data will be collected for study purposes other than data needed to keep track of their withdrawal. If they withdraw from the study all data and samples that have already been collected for study purposes will be used unless a written request for all data to be destroyed is received. Participants who withdraw from the study will discontinue all study procedures.

Benefits

A number of potential health benefits that may accrue to participants and important scientific knowledge will likely result from this work. We expect that participants will achieve lifestyle modifications that could be sustained as a part of their personal health regimen in the setting of their community environment. Additionally, information collected from this study will benefit others through a greater understanding of how to best maintain physical function following an intensive weight loss intervention.

6 Statistical Plan

This is a pilot study that will be used to generate preliminary data for a larger clinical trial. The data analysis for both Aims are outlined below:

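### Aim 2 schedules no adverse-event question and stops new data at withdrawal with no safety exception, so harms among the roughly 30% expected to drop out may be under-counted

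*Combined protocol and SAP*

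**What the plan says.** **How events come to light.** In Section 5 (Risk/Benefit Assessment, Physical Risks), participants receive the team's contact details and are "encouraged to communicate with them about any concerns regarding any aspects of the study". Events that are reported go into a log. The same paragraph then undertakes that staff will record and regularly review every health occurrence, but gives no question, form or schedule for finding them. Exertion ratings are requested during exercise classes. Table 4 has rows for function, steps, weight, diet, questionnaires, satisfaction, feedback, attrition, feasibility, adherence and retention. It has none for falls, injury, new symptoms or unplanned care. Once the tablet and watch have been handed over, "All additional interaction will occur virtually".

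**What happens at withdrawal.** Section 5 (Alternatives to Participation) states that "no new data will be collected for study purposes other than data needed to keep track of their withdrawal" and that "Participants who withdraw from the study will discontinue all study procedures". Earlier data are retained: "all data and samples that have already been collected for study purposes will be used unless a written request for all data to be destroyed" reaches the team. Section 4.3.1 adds that a participant may be withdrawn if he or she "cannot be contacted by the study staff after initial contact".

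**What is reported.** Section 7 sends serious events, related or not, to the IRB within 24 hours of the team learning of them, together with a count of adverse events and of withdrawals. It also describes the study as not being an intervention and expects adverse events to consist only of breaches of health information.

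**How many are expected to leave.** Section 5, Aim 2 sets the target, "We will enroll participants until we reach a total of 10 study completers", and then gives the allowance for people leaving: "We anticipate enrolling approximately 15, allowing for a 30% dropout rate".

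**The concern.** Harm is a plausible reason for leaving an exercise programme. If nobody asks about harm on a schedule, and recording ends when a person leaves, the missing safety data may be concentrated among those most likely to have been harmed. The 24-hour rule in Section 7 cannot act on an event that the team never hears about.

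Two results would suffer. The adverse-event count sent to the IRB could be too low. Attrition, which Aim 2, Table 4 and Section 6 use to measure acceptability (part of a primary endpoint in Section 3.2), would mix people who left because of harm with people who left for convenience. Section 6 presents the pilot as a source of preliminary data for a larger trial, so both results could mislead its planning.

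**Working it through.** **1. The plan's enrolment figure.** Inputs from Section 5, Aim 2: 10 completers and 30% dropout. Enrolment = 10 / (1 − 0.30) = 14.3, rounded up to 15. The stated figure reproduces. With 15 enrolled and 10 completing, 5 leave: 5/15 = 33%, against the stated 30%.

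**2. Planned follow-up left unobserved.** Section 5 and Table 4 give 12 weeks of follow-up, so 15 × 12 = 180 person-weeks are planned. If 5 people leave at week t, the loss is 5 × (12 − t) person-weeks. The documents do not say when people leave, so t is assumed.

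| Week of leaving (assumed) | Person-weeks lost | Share of 180 | Share if exactly 30% leave, 0.30 × (12 − t)/12 |
|---|---|---|---|
| 0 | 60 | 33% | 30% |
| 3 | 45 | 25% | 22.5% |
| 6 | 30 | 17% | 15% |
| 9 | 15 | 8% | 7.5% |

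**3. What this does to a count.** Assume a 12-week risk p of at least one event per participant, a constant hazard, departure at week 6 unrelated to harm, and full capture while people are in the study. The expected number of participants with an event is 15p under full follow-up, and 10p + 5 × [1 − (1 − p)^0.5] when recording ends at week 6 for five of them.

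- p = 5%: 0.75 falls to 0.63.
- p = 10%: 1.50 falls to 1.26.
- p = 30%: 4.50 falls to 3.82.

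The shortfall is about 15% to 16% throughout. It would be larger if people with events were more likely to leave, or if the passive route missed events among those who stay. The documents give no figure for either.

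**4. The safety text set side by side.** Section 7 says the study is not an intervention; Section 5, Aim 2 describes a 3-month pilot intervention. Section 7 expects only data-loss events; Section 5, Physical Risks names fatigue and muscle soreness as the most common consequences of physical activity. A safety section that does not anticipate physical events gives staff little prompt to look for them.

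**5. The withdrawal text.** The only data allowed after withdrawal are those needed to track it. Nothing requires a reason, asks about health events, or provides for following an event still open at that point.

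**The case against.** A reader might infer that events are logged only when a participant volunteers them. The text does not go that far. Section 5 promises to record all health occurrences, instructors ask about exertion in class, and staff guide the assessments by video at weeks 0, 6 and 12. These contacts give staff chances to hear of a problem. What remains is that no method or schedule is written down. An exertion rating is not an adverse-event question, and it cannot reach someone who has stopped attending.

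A reader might also infer that an injured person who quits simply disappears from the safety record, or that collection ends at loss of contact. Neither is established. An injury reported before or on leaving is logged and kept, unless destruction of the data is requested in writing. Section 7 does not exclude withdrawn people from serious-event reporting once the team learns of an event. Tracking data could include a reason. Withdrawal for non-contact is discretionary.

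Two further limits are fair. The consent pages are not available here, so any permission for safety follow-up in them cannot be seen. The programme itself is still to be designed in Aim 1b, so session detail is not yet expected. Neither limit removes the gap in Table 4 or the withdrawal rule as written.

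**Conclusion.** The point stands as one about ascertainment. Aim 2 has no scheduled adverse-event query, its promise to record all health occurrences has no method, and new data stop at withdrawal without a safety exception. The likely direction is an under-count among about 5 of 15 participants. Its size is unknown. Unobserved planned follow-up is about 17% if they leave at week 6, with a range of 8% to 33% for assumed departure between week 9 and week 0.

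It would be wrong to conclude that a third of harms are lost: that share of follow-up goes unobserved only if everyone who drops out leaves at the start. Nor should the zero-event upper limits be compared as if the five leavers were never seen. The one-sided 95% limits are 1 − 0.05^(1/15) = 18% and 1 − 0.05^(1/10) = 26%, but the second gives leavers no observed time although their earlier data are kept. Section 6 also plans no interval for adverse events. A rate per observed person-week would be biased only if leaving were related to harm or capture were incomplete; the plan states a count and no denominator.

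The dropout figure applies to Aim 2 only and covers leaving for any reason. No planned analysis of function is invalidated. The safety count and the meaning of attrition are what become hard to read.

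**What to change.** 1. In Table 4, add a short fixed adverse-event question set (falls, injury, new symptoms, unplanned care) to the existing week 6 and week 12 virtual sessions. It could optionally also appear as a self-report item beside the weekly weight entry.
2. In Section 5, Alternatives to Participation, amend the withdrawal rule so that the withdrawal record includes the reason and any health event, and events open at that point are followed up with the participant's agreement.
3. In Section 6, report harm-related withdrawals separately within attrition.
4. Reconcile Section 7's statements that the study is not an intervention and that adverse events will be confined to data loss with the Aim 2 intervention and the Physical Risks text in Section 5.

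The cost is a few minutes per session, a few questionnaire items, and protocol and consent wording. The recorded adverse-event count will probably be higher, and that should be read as better capture.

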Setting: Screening will be conducted by telephone. Consents will be sent electronically and a consent presentation will be conducted virtually using Duke Zoom. Consented participants will come to the Duke Center for Living Stedman Center and will complete SPPB and 6-minute walk to determine their group assignment based on functional outcomes (Table 2). Next, using telephone or Duke Zoom, participants will undergo a guided semi-structured interview (sample interview guide for both groups below).

Table 2. Aim 1a Participants

Groups	Criteria	Social Cognitive Theory
Maintainers	Physical function improvements were maintained	Personal, environmental, and behavioral facilitators
Non-maintainers	Physical function improvements were regressed	Personal, environmental, and behavioral barriers

Note to IRB: This is an interview guide for semi-structured qualitative interviews of participants as laid out in the study protocol. The interviewer will use this guide to organize the interview. Because it is a guide, exact questions may vary during the course of the interview or order may vary somewhat depending on answers given by participants. However, the guide provides a general structure and order for questions and ensures that all domains are covered in the interview as appropriate, based on the answers of the participant being interviewed. The interviewer will adhere to the guide, but will also follow the conversation, which may stray from the guide as he/she feels is appropriate.

Sample semi-structured interview guide for the Maintainers

1. Personal

1. Do you see yourself differently than you did before or during the study?
2. How does it feel to have maintained your weight loss/function status?
3. What is your definition of success, as it relates to your weight or health?
4. What's one thing that is contributing to your success of maintaining weight loss/continuing to eat healthy?
5. When you think of other goals you have achieved, what about you do you believe helped you to achieve them?
 1. Can you describe a personal attribute that helped you maintain your weight loss?
6. How do you feel about your body? About your health?

2. Behavioral

1. What activities reinforce your motivation to eat healthy meals and/or move your body?
2. What behaviors have helped you be successful?
3. How have your behaviors changed since completing the study?
4. Describe the process of changing your behavior long term.

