5. What were your expectations of losing weight? Were those expectations met?
6. Has COVID-19 impacted your ability to maintain your nutrition and physical activity habits? If so, how? If not, why?

3. Environmental

1. What outside yourself helps you to maintain your weight loss or achieve other goals?
2. What outside yourself is crucial to your success?
3. Describe the support outside of yourself that helps you maintain activities/choices that support your health?
4. Did you experience an event, idea, or person that reinforced your commitment to maintaining weight loss?
5. How does your culture/community affect your eating/exercise habits?
6. How does your family/friends influence your behavior?
7. How did your social support network (friends, family, colleagues) react to your weight loss?

Sample semi-structured interview guide for the Non-maintainers

Personal

1. What thoughts do you have about your weight journey since you completed the study?
2. How do you feel about your body? About your health? About your current weight?
3. What about your personality or experiences affects your health/nutrition choices?
4. What has worked for you in the past regarding _____ (exercise, weight loss, diet)?
5. Has there been a time when you were successful and how did that make you feel?
6. If you could change one thing today regarding your health, what would that be?
7. Is there anything about your health or your weight that concerns you?
8. Describe your approach to other goals you have
 - a) Why do you think you were able to achieve those goals?
 - b) Why do you think you were not able to achieve those goals?

Behavioral

1. Have you maintained any habits that you acquired during the study? Why or why not?
2. Do you cook and if so, do you enjoy it?

a) If so, how would you describe your cooking skills?

Beginner/intermediate/advanced/expert

3. What about diet is important to you?
 - a) What health habits are important to you?
4. What concerns, if any, do you have about your current level of physical activity?
5. What concerns, if any, do you have about your current eating habits?
6. When you tried _____ (dieting, Eggspsdite) in the past, what got in the way?
 - a) If it was a person - what would it take to get them on board with your habit changes?
 - b) If it was finances/access to food - have you ever used community resources to help improve your access to food?
7. Describe your personal process of trying to adopt long lasting behavior change.

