Aim1a: A qualitative analytical approach is well suited to exploring concepts related to a complex process (long-term adherence to weight loss and physical activity). We plan to use applied thematic analysis, organizing the data in response to the a priori questions contained in the semi-structured interviews and interview guides. Interview guide questions will be developed utilizing input from the Interventionist and socio-behavioral researchers. We will use applied thematic analysis to analyze the data. Audio recordings will be transcribed verbatim following a transcription protocol. Two analysts will use NVivo 12 software to develop and apply structural (a priori) codes to segment participants' narratives into conceptual categories (e.g., all text describing a similar concept, such as psychosocial factors). Next, analysts will identify and apply content-driven (emergent) codes to the text for each of the conceptual categories (e.g., potential themes related to psychosocial factors). Inter-coder reliability assessments will be conducted on approximately 25% of transcripts during both structural and content coding. Discrepancies in coding will be resolved through analyst discussions; transcripts will be re-coded and the codebook revised accordingly. Once coding is complete, we will examine code frequencies across transcripts to identify salient factors for each interview group, followed by comparing and contrasting factors between groups. To conclude analyses, analytical memos and reports will be written, describing the factors influencing success in maintaining the functional benefits of obesity treatment over time, together with illustrative quotes.

Aim 2. Feasibility: Proportion of participants recruited will be calculated as the number of participants deemed potentially eligible and contacted for enrollment divided by the total number of participants enrolled. Proportion retention will be computed by dividing the number

of retained participants at the end of the intervention by the total number randomized into the study. Fidelity: Proportion adherent to the tele-nutrition diet and tele-exercise intervention. Acceptability: Levels of attrition will be calculated and satisfaction will be assessed with survey items on a Likert-scale and focus group.

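### Aim 1a contrasts factors between Maintainers and Non-maintainers, but only Non-maintainers are asked directly about barriers, so a barrier common to both can look specific to one group

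*Combined protocol and SAP*

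**What the plan says.** Section 5, Table 2 sorts Aim 1a participants by whether functional gains were kept. Its Social Cognitive Theory column lists "Personal, environmental, and behavioral facilitators" for Maintainers and "Personal, environmental, and behavioral barriers" for Non-maintainers. Aim 1a in Section 2 makes the same division. Two guides follow, headed "Sample semi-structured interview guide for the Maintainers" and "Sample semi-structured interview guide for the Non-maintainers". Maintainers are asked, for example, "What outside yourself is crucial to your success"; Non-maintainers are asked "What do you feel are your main barriers to healthy eating/exercise".

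Section 6 describes an applied thematic analysis, "organizing the data in response to the a priori questions contained in the semi-structured interviews and interview guides". After coding, "we will examine code frequencies across transcripts to identify salient factors for each interview group, followed by comparing and contrasting factors between groups". For the Aim 2 feedback session, Section 6 says the approach is similar but without the group comparison, which confirms that the comparison is a separate step in Aim 1a. Section 6 neither limits that comparison to shared questions nor mentions that the guides differ.

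**The concern.** How often a code appears depends on how common the factor is and on whether participants were asked about it. If only one group is asked about barriers, salience in that group partly reflects the question. Tailored guides are a reasonable way to describe each group separately. They are a weak basis for saying that a factor separates the groups.

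Interview feedback is listed among the primary endpoints (Section 3.2), and the findings inform the Aim 1b programme. A barrier that Maintainers also met and overcame is useful design information. Under this plan it could be recorded as a characteristic of Non-maintainers, and how Maintainers dealt with it might never be asked.

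**Working it through.** **1. Content of the guides.** I classified each numbered question in Section 5. The classification is a judgement, but moving one or two items does not alter the conclusion.

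| Type of question | Maintainers | Non-maintainers |
|---|---|---|
| Asks what helped, or about success | 8 | 3 |
| Asks about barriers | 0 | 2 |
| Asks about concerns | 0 | 3 |
| Two-sided | 0 | 2 |
| Neutral | 11 | 12 |
| Total | 19 (6 + 6 + 7) | 22 (8 + 9 + 5) |

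The COVID-19 item is in both guides and is counted as neutral; for Maintainers it is the nearest thing to a barrier question. For Non-maintainers, barrier, concern and two-sided items together give at most 2 + 3 + 2 = 7 of 22 (32%). Items that invite an answer about what helped give 3 + 2 = 5 of 22 (23%). The Maintainers guide has 8 of 19 (42%) on what helped and none explicitly on barriers. The clear gap is therefore on the barrier side.

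**2. Size.** The plan gives no figure to reproduce for this point. Its group size is 12 to 15 (Section 5, Aim 1a). The mention rates below are assumptions, and so is the gap of 4 participants, since the plan has no counting rule.

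Take a barrier equally common in both groups. Let X be the number of Non-maintainers who mention it when prompted, Binomial(12, 0.8). Let Y be the number of Maintainers who mention it unprompted, Binomial(12, q). The expected count is 12 × 0.8 = 9.6 for Non-maintainers and 12q for Maintainers. The chance of a spurious gap is

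P(X − Y ≥ 4) = Σ P(X = a) P(Y = b), summed over all a − b ≥ 4.

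| Unprompted rate q | Expected Maintainers (12q) | Expected gap (9.6 − 12q) | P(gap ≥ 4) |
|---|---|---|---|
| 30% | 3.6 | 6.0 | 88% |
| 40% | 4.8 | 4.8 | 73% |
| 50% | 6.0 | 3.6 | 52% |
| 60% | 7.2 | 2.4 | 31% |
| 70% | 8.4 | 1.2 | 14% |

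With equal questioning, the same formula gives 4% when both rates are 80% and 8% when both are 50%. With 15 per group and a gap of at least 5, the result is 90% at q = 30%, falling to 10% at q = 70%. Equal questioning at 50% in both groups then gives 5%.

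**3. Check with a different model.** Suppose 60% of each group truly face the barrier and 90% of those mention it when asked. If 70%, 50% or 30% of them mention it unasked, a gap of at least 3 of 12 arises 33%, 57% or 80% of the time, against 15% with equal questioning. Over true prevalence of 40 to 80% and 12 to 15 per group, the range is 25 to 97%, against 13 to 18%. Both models agree on direction; neither fixes the size.

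**The case against.** The strongest reply is that the guides are less one-sided than Table 2. Over half of each guide is neutral (11 of 19 and 12 of 22). About eight topics are in both: body and health, other goals, the process of behaviour change, expectations, COVID-19, culture and community, family and friends, and the network's reaction. Several of these let Maintainers volunteer barriers, so unprompted rates of 60 to 70% are plausible and the distortion may be modest. That stands, and it is why a range is shown.

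The guides are also labelled samples, and the interviewer may depart from them. This carries less weight: Section 5 also says the interviewer will keep to the guide, and freedom to stray does not ensure that Maintainers are asked about barriers.

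Some stronger readings are tempting but unsupported:

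- A reader might infer from Table 2 that Non-maintainers are asked mainly what went wrong. At most 7 of 22 questions do this, and others ask what worked, about past success and about sources of support. For the same reason, facilitators are unlikely to be missed among Non-maintainers to a similar degree.
- A reader might take Section 6 to compare frequencies directly. It uses them to pick salient factors within each group and then contrasts the factors. The distortion still carries through the selection step.
- A reader might suppose that the contrast decides the Aim 1b content. Aim 1b and Section 5 combine the interviews with the established intervention, the team's experience and outside experts, so the contrast is one input.

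**Conclusion.** The concern holds in a limited form. Followed as written, the plan can make a barrier shared by both groups look specific to Non-maintainers, because only they are asked for barriers explicitly and Section 6 has no safeguard. The direction follows from the documents. The size does not: the 14 to 88% range rests on an assumed 80% prompted rate, unprompted rates of 70 down to 30%, equal true prevalence, independent participants and a reviewer-chosen gap of 4 of 12. The top of that range should not be quoted alone. For an exploratory aim in a pilot this does not undermine the within-group descriptions. It is still worth correcting before interviews start, because answers to questions never asked cannot be recovered from the transcripts.

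**What to change.** 1. Add to the Maintainers guide one open question in each domain (personal, behavioral, environmental) on what made it harder to keep up the gains.
2. Check that the Non-maintainers guide has a matching question on what helped in each domain. The personal and environment domains largely have one. In the behavioral domain the nearest item is the two-sided question on habits kept.
3. Add to Section 6 that statements about whether a factor distinguishes the groups rest on topics asked of both, and that factors raised only by group-specific questions are reported as within-group description. Relevant remarks volunteered elsewhere on a shared topic can still be used; restricting the whole contrast to answers to identical questions would discard them needlessly.

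The cost is three questions for Maintainers, perhaps one for Non-maintainers, a sentence in Section 6 and slightly longer interviews. Section 6 describes the guide questions as still to be developed, so there is room for the change.
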